Weekly contact by study staff (phone or email per participants' choice): Study staff will maintain regular contacts in the mode of participants' choice during the 12 weeks of the intervention. This is intended to help with retention as well as monitoring for adverse events. Study staff will collect data about minutes of physical activity during these weekly phone contacts. No survey or other data will be collected during this contacts, unless a participant verbalizes a physical or psychological adverse event.

Study Visit #7 (Intervention Week 6): Participants will be asked to complete questionnaires at the midpoint of the 12-week intervention at home electronically (if they have computer access at home) or in paper/pencil form (for those without sufficient comfort levels or access to a computer~~to~~RA will pick them up at participants~~to~~ next class).

Study Visit #14-- Last visit during pregnancy: Participants will complete another set of questionnaires electronically or in paper/pencil format. A blood sample will also be collected (8 ml blood by venipuncture in 2 EDTA [purple top] tubes).

Study Visit #15-- Postpartum Visit/Interview Session: Each participant will meet with study staff (RA, PD, and/or PI) to complete the questionnaires and participate in a semi-structured interview. Specific questions for this semi-structured interview are found in the Study Interview Guides/Scripts document. This interview will be audiotaped (and later transcribed).

Note: if a participant chooses to withdraw from the study, they will be given the opportunity to give their reasonings for withdrawal in the form of a short interview with research staff.

**** For Addendum Feb 2018: "Long-Term Follow-Up" study visit:** participants who "opted-in" to being contacted for future study will be contacted via email and/or phone about answering survey questions. Participants will give consent via REDCap (or in rare instances, may choose paper & pencil, which will be completed in-person with the research nurse) and will answer survey questions, using the same measures that have been used at previous study visits.

STUDY MEASURES

** SEE TABLE 1. STUDY MEASURES BY TIMEPOINTS

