VCU Site Details

1. * Select all VCU sites that will be utilized in this study:

Children's Hospital of Richmond at VCU

Clinical Research Services Unit (CRSU)

Massey Cancer Center

VCU Health Community Memorial Hospital

VCU Medical Center downtown

VCU Monroe Park Campus

VCU Qatar

Other VCU Site

2. * Provide details regarding each VCU Site including:

- what clinics / facilities will be used

- resources that are available for the conduct of this study:

Upon IRB approval, recruitment materials will be posted in selected places throughout the recruitment area, such as healthcare providers' offices (obstetric, primary care, and mental health practices), community centers, and publicly accessible internet websites (e.g. electronic methods of advertisement in VCU media- VCU TelegRam, digital message boards). VCUHS clinics serve nearly 2,200 pregnant women per year who are potentially eligible for this study. The Project Director (PD) and Research Assistant (RA) will keep a list of any patients who contact the study office who are not interested, so that these patients will not be approached in clinic.

Study visit #1 will occur at a quiet, private location for the baseline surveys and blood draws to be done as well as the participant-PD meeting (for motivational interviewing, goal setting, etc). This is most likely occur in the research space at the VCU School of Nursing, unless there is a reason that the participant cannot access that location. In that case, the RA and PD will arrange to meet them in a quiet, private, safe mutually convenient location-- for example, the participants' obstetricians' office.

Study visits #2-13: yoga classes will be offered at a yoga studio in the community (4025 Yoga & Wellness) that is near a bus line and has easy parking, thus is easily accessible. Participants in the study will be the only participants in the yoga classes (i.e., there will not be any other non-participants taking the group classes). No staff at the yoga studio will be involved in the study or with study participants in any way.

Study visit #14: again, will occur in a quiet, private location for participants to complete the surveys and blood draw; most likely this will occur at the VCU School of Nursing research space.

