- 5. * Is it likely investigators could discover a participant's previously unknown condition (eg disease, suicidal thoughts, wrong paternity) or if a participant is engaging in illegal activities:**

Yes
 No

- 6. If yes, explain how and when such a discovery will be handled:**

During screening: if an individual contacts study staff and is ineligible for the study but has a concerning psychological risk (e.g. high score on the PHQ9 (or endorses suicidality) or signs of psychosis or mania), she will be provided with phone numbers to the crisis/emergency response teams of local mental health agencies (Henrico County Community Services Board: [contact]; Chesterfield County Community Services Board: [contact]; Richmond Behavioral Health Authority: [contact]) and/or will be directed for emergent care at the local emergency department.

For participants: It is possible that some participants will experience increased intrapersonal or interpersonal psychological distress as a result of participating in assessment or intervention. In the vast majority of cases, we believe that any increased distress experienced will be mild and transitory in nature.

IF Significant worsening of depressive symptoms= participant scores ≥ 20 on the PHQ9 (with no endorsement of suicidality) --> PI will contact participant and conduct the MINI suicide module as soon as information is obtained. If suicide risk is low ($=8$), applicant will ask participant to be in touch with her healthcare provider. Contact information for local resources will be provided, as needed (e.g. Henrico County Community Services Board: [contact]; Chesterfield County Community Services Board: [contact]; Richmond Behavioral Health Authority: [contact]; local emergency departments).

IF endorsement of suicidality item on PHQ9 or verbal report of suicidality --> PI will contact participant and conduct the MINI suicide module as soon as information is obtained. If suicide risk is high ($=9$), PI will ensure participant is accompanied by a family member or friend to their healthcare provider or local emergency department for immediate evaluation. PI will contact study team and clinical psychologist Co-I ([name]) and/or psychiatrist-collaborator ([name]) to assess the concern (within 1 day).

See also page 8 on the DSMP.

- 7. * Describe any potential risks or harms to a community or a specific population based on study findings:**
n/a

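### Week-6 paper questionnaires are returned only at the next weekly class, so a written PHQ-9 safety trigger may go unread for 0 to 7 days (7 to 14 if one class is missed)

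*Combined protocol and SAP*

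**What the plan says.** All references are to the combined protocol and SAP.

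- **Return of paper forms.** Research Description, item 4, Study Visit #7 (Intervention Week 6): questionnaires are completed at home, electronically or on paper. For paper, the text says "RA will pick them up at participants~~to~~ next class" (the stray characters come from text extraction). No other return route is named.
- **When the safety response starts.** Risks, Discomforts, Potential Harms and Benefits, item 6, has two triggers. One is "participant scores ≥ 20 on the PHQ9 (with no endorsement of suicidality"). The other is introduced by "IF endorsement of suicidality item on PHQ9 or verbal report of suicidality". Under both, "PI will contact participant and conduct the MINI suicide module as soon as information is obtained".
- **The one-day limit.** It appears only in the second branch. After suicidality is known and risk is rated high, the investigator contacts the team and the clinical psychologist or psychiatrist "to assess the concern (within 1 day").
- **The other model time points.** VCU Site Details, item 2, says visit #1 "will occur at a quiet, private location for the baseline surveys and blood draws to be done" and visit #14 "will occur in a quiet, private location for participants to complete the surveys and blood draw". For visit #15, Research Description, item 4, says "Each participant will meet with study staff (RA, PD, and/or PI) to complete the questionnaires".

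**The concern.** The PHQ-9 is a safety instrument here as well as the main Aim 2 outcome. The description of the measure under Research Description, item 4, assigns its suicide item to adverse-event monitoring. A safety instrument protects the participant only once someone has read it. Of the four time points in the Aim 2 model, week 6 is the only one at which the text places completion away from a staffed visit, and for paper users it then leaves the form with the woman until a class.

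The triggers are plausible in this population. Entry requires a PHQ-9 of at least 10 and sets no upper limit, so a score of 20 or more is not remote. Suicidal ideation is excluded at entry but can arise later, and the plan provides for that. What is at stake is how promptly the team acts on a written endorsement or a high score that the woman has not also spoken about. Any effect on the week-6 outcome data is secondary and of unknown direction.

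**Working it through.** The plan states no delay from completion to reading, so there is no figure to reproduce. The delay follows from the class schedule.

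**Inputs**
- Class interval: 7 days. Visits #2 to #13 are 12 weekly classes (Research Description, item 4).
- Visit #7 is the sixth class, since 7 − 1 = 6. Six classes remain, so a next class always exists.
- Pick-up point: the next class (week-6 paragraph).
- PHQ-9 at week 6: inferred. Data Analysis Plan, Aim 2, makes the PHQ-9 the primary variable and lists week 6 as a model time point; specific aim 2 also names the midpoint for depressive symptoms. Table 1, which would settle this, is not in the text available.

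**Formula.** Let t be the days between the most recent class and completion (0 ≤ t ≤ 7), and k the number of classes then missed. Days from completion to pick-up = 7(k + 1) − t.

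- k = 0: 7 − t, which runs from 0 to 7 days.
- k = 1: 14 − t, which runs from 7 to 14 days.
- If completion is spread evenly over the week (an assumption), the mean of t is 3.5. The mean delays are then 7 − 3.5 = 3.5 days and 14 − 3.5 = 10.5 days.

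These are times to reading only if the form is checked at pick-up. No limit from pick-up to scoring is stated. An assumed further lag of 1 day would give 1 to 8 days (8 to 15 with one missed class). A lag of 3 days would give 3 to 10 days (10 to 17).

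**Does anything else in the text bring the form to a reader sooner?**
- The weekly contact (phone, text or email) asks about physical or psychological concerns. It gathers no survey data unless the woman voices an adverse event.
- A verbal report triggers the same response as a marked item, but depends on her speaking up.
- Paper home logs are collected weekly by the research assistants. The text does not say that the week-6 questionnaires travel with them.
- The week-6 gift card is tied to completion of that assessment, and staff are trained on elevated depression scores. Neither sets a reading time.

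These safeguards can reveal a problem that a woman mentions. None of them scores the PHQ-9 or finds an endorsement that she wrote but did not say.

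**The case against.** The strongest reply is that the deciding documents are not available. Item 6 of the Risks section refers on to the data safety monitoring plan, and Retention and Adverse Event Monitoring refers to a separate adverse-event protocol. Both are listed as approved. Handling time for an elevated form is what such files, or the manual of operations, would be expected to contain. This stands, and it makes the point conditional. It does not remove it, because the week-6 paragraph states a definite collection rule that, followed as written, produces the delay.

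A reader might infer that the plan breaks its own one-day limit. It does not. That limit times a consultation after suicidality is known. It does not apply to a score of 20 or more without suicidality, and it sets no deadline for reading forms.

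A reader might also want a percentage of women exposed. The documents give neither an attendance rate nor the share using paper. The withdrawal criterion about attending a majority of sessions is a compliance floor, not an expected attendance rate. No percentage can be supported.

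Electronic users also complete week 6 at home, and the text gives no review time for REDCap entries. That is fair, but it is silence about a form the staff can already open. For paper, a stated rule keeps the form out of their hands.

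Finally, weekly collection of paper logs is not tied to class attendance, so a research assistant might recover a form after a missed class sooner than 7 to 14 days. That is possible, but the text does not provide for it.

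**Conclusion.** The point holds in a limited form. On the text available, a paper user's written suicide endorsement or score of 20 or more at week 6, if not also voiced, may go unread for 0 to 7 days after completion, or 7 to 14 days if one class is missed. These ranges need only weekly classes, pick-up at the next class attended and reading at pick-up; they do not depend on any assumed attendance rate.

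The conclusion rests on three conditions: the PHQ-9 is in the week-6 set, no other return route is used, and no unseen document already sets a reading deadline. The number of women affected is unknown and probably small, and the number who would have a positive trigger cannot be estimated. The documents do not show that any safety rule is breached, or that the study has no deadline at all. This is a cheap patient-safety improvement worth making, not a threat to the trial's conclusions.

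**What to change.** Amend the Study Visit #7 paragraph so that paper users complete the PHQ-9 on the day of the week-6 class, either at home and bring it, or at the studio. The research assistant checks the suicide item and the total score that day and passes any trigger to the investigator the same day. The other week-6 questionnaires can stay on next-class pick-up, and the response rules in item 6 of the Risks section need no change.

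If a paper user misses that class, staff contact her that week to arrange prompt return of the form. Alternatively, they ask the PHQ-9 by phone, flagged in the data as a different mode and written in as an exception to the sentences that bar survey data at the weekly contacts (the weekly-contact paragraph of Research Description, item 4, and Retention and Adverse Event Monitoring).

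The cost is a few wording changes, a brief same-day check by existing staff, and somewhere private at the studio for women who complete the form there. The downside is a small change of setting or mode for a few women at one time point. If the data safety monitoring plan, adverse-event protocol or manual already sets a reading deadline for these forms, it is enough to cite it in the week-6 paragraph.

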2. Examine the preliminary effects of the MOMP intervention on measures of maternal psychobehavioral factors (i.e., depressive symptoms, anxiety, ruminations, PA self-efficacy, attachment) at baseline, midpoint and end of the 12-week intervention, and at 6-weeks postpartum and at 10-20 months postpartum, and on baby♦'s birth weight, compared with archival data from depressed women receiving the UC, to estimate effect sizes to inform future studies.
3. Identify DNA methylation (DNAm) patterns associated with chronic depressive symptoms during pregnancy and investigate whether participation in the MOMP intervention targets these patterns: This aim will be accomplished by evaluating both genome-wide and gene-specific DNAm patterns (e.g., candidate genes putatively related to depression, pregnancy, and mindful interventions: Nr3c1, NGFI-A, FKBP5, BDNF, TrkB, HP1BP3, TTC9B). These patterns will be compared with patterns in recently collected archival data from pregnant women with and without depressive symptoms receiving UC.

3. * Describe the study's background and significance, including citations, or upload a citation list in document upload. Use lay language whenever possible.

Chronic and recurrent depressive symptoms are a significant public health problem.¹ Women with chronic depressive symptoms face significant treatment challenges during pregnancy. Close to 20% of women experience clinically significant depressive symptoms during pregnancy (e.g., feelings of sadness, anhedonia, sleep alterations, and fatigue, among others),² with the majority manifesting a recurrence of symptoms rather than a new onset.³⁻⁵ Although there are numerous pharmacological treatments available for depressive symptoms, data are conflicting with respect to safety of antidepressant medications during pregnancy and there is little research addressing efficacy of non-pharmacological therapies in this population.^{3,6,7} Currently, no therapies are universally effective at decreasing depressive symptoms and uniformly accepted as low obstetrical and fetal risk.^{8,9} Further, many pregnant women are concerned about stigma, side effects, fetal effects, and/or costs of the ♦usual care♦ (UC: antidepressants, psychotherapy) for symptoms and elect to avoid or decrease UC during pregnancy.¹⁰⁻¹⁶ Hence, many women with depressive symptoms remain un- or under-treated.³

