(a) **Depressive symptom severity:** Depressive symptom severity will be evaluated using the Patient Health Questionnaire (PHQ-9), a widely used instrument which has been validated during pregnancy.¹⁶⁹ The PHQ-9 includes self-report items regarding depressive symptoms over the past two weeks. Total scores range from 0-27: 0-4 indicates minimal depression, 5-9 mild depressive symptoms, 10-14 moderate depressive symptoms, 15-19 moderately severe depressive symptoms, and =20 severe depressive symptoms. For analysis purposes, presence of depressive symptoms will be defined as a score =10 on the PHQ9. The PHQ-9 includes a question on suicidal ideation,^{202,203} which will be used for monitoring for adverse events as described in the Protection of Human Subjects section. Because the archival comparison group database includes the Edinburgh Postnatal Depression Scale (EPDS)¹⁸⁰ in the pregnancy and postpartum assessment, we will also administer this survey at the same timepoints. The EPDS is a widely used and validated measure of depressive symptoms, with 10 questions appropriate for the prenatal and postpartum woman; a score =10 (range 0-30) suggests possible depressive symptoms. Guidelines regarding management of participants with depressive symptoms or suicidal thoughts are detailed in the Protection of Human Subjects section but in brief, the researchers will be poised to assess further and make referrals to appropriate community organizations, healthcare providers, or emergency departments in cases of psychological distress (score =20 on PHQ9 and/or suicidal ideation) or physical injury. (b) **Stress:** The Perceived Stress Scale-10 (PSS-10), a widely used, psychometrically sound instrument, will assess the degree to which a participant perceives stress in her life during the past month.¹⁸¹⁻¹⁸⁵ The PSS-10 asks respondents to report about feelings such as unpredictability, uncontrollability, and overloading of stress in their lives; scores range from 0-40; higher scores correspond to a higher perceived stress level.¹⁸⁴ (c) **Anxiety:** Current levels of anxiety (state anxiety) will be evaluated with the State-Trait Anxiety Inventory, Form Y (STA). This study focuses specifically on state anxiety, as this score is sensitive to women's anxiety during pregnancy and is more likely to demonstrate change within an intervention period.^{190,204} This measure yields reliable and valid scores.¹⁸⁷⁻¹⁸⁹ The STA scores range from 20-40, with higher scores representing higher levels of state anxiety. (d) **Rumination:** Rumination, or repetitive self-critical thinking, will be evaluated with the 10-item Ruminative Responses Scale (RRS) which assesses the propensity to ruminate in association with sadness or depression. A psychometrically sound and widely used instrument, the RRS asks respondents to rate how often they experience various aspects of rumination.¹⁹³ The RRS has two factors of brooding (self-critical pondering) and reflecting (emotionally-neutral pondering or brainstorming). (e) **Self-Efficacy for Physical Activity:** The Physical Activity Self-Efficacy Scale (PASES)^{194,195} is an eight question scale which contains items about SM of physical activities and social support regarding PA. This psychometrically sound scale was selected because of its specific focus on SM of PA. Originally designed for adolescents, the wording has been slightly adapted for an adult sample. (f) **Maternal-Fetal/Child Attachment:** The Maternal-Fetal Attachment Scale (MFAS)^{32,198} assesses the extent to which women have an affiliation and interaction with their unborn child (during pregnancy) and their infant (during PP). Maternal depression has a proximal effect on maternal-child attachment,¹⁷ hence it is highly relevant to evaluate attachment in relation to an intervention designed to address depression.

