Comparison Group Data: Archival data from an existing IRB-approved study (NIMHD2P60MD002256, PI: [name]) includes pregnant women recruited from the VCUHS and area clinics who did not receive the MOMS intervention yet were followed throughout their pregnancies and into the postpartum period, using psychobehavioral, birth weight, and DNAm measures identical to those proposed in this study. The de-identified data will be used to form two age/race-matched comparison groups: (a) positive comparison group (n=40): pregnant women with clinically relevant depressive symptoms receiving the UC; and, (b) negative comparison group (n=40): pregnant women without clinical depressive symptoms. The timelines of these studies align well; as of May 2015, the study has enrolled approximately 135 women (50% AA) with ~15% of the sample endorsing depressive symptoms (unpublished data). Data collection from the total expected sample (n=220) will be completed by early 2017, at which point the proposed study will be ready to derive the comparison groups for analysis. To facilitate longitudinal comparisons across the two studies, the pre-/post-intervention data for the proposed study will correspond to data collected early in the second trimester of pregnancy (approximately 12-22 weeks gestation) and late in second trimester/ early in third trimester of pregnancy (approximately 24-34 weeks gestation) respectively, in the comparison study, represented in Figure 2.

Data Analysis Plan

Aim 1: Evaluate the feasibility and acceptability of the MOMS intervention for chronic depressive symptoms during pregnancy: (a) Data related to recruitment, retention and adherence to the MOMS intervention will be analyzed using descriptive techniques, including percentages and means. The number of participants who complete each time point will be recorded and percentages of the following calculated: persons eligible to participate; persons who signed a consent form; and PA sessions attended, home PA participation, and participant attrition. Reasons for attrition will be described.

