Aim 2: Examine the potential effects of the MOMS intervention on measures of maternal psychological symptoms assessed at multiple time points (Table 1) and on the baby²⁰⁶s birth weight, with the primary variable of interest, depressive symptoms, measured by the PHQ-9. Means, variances and covariances/ correlations along with 95% confidence intervals for each of the three groups (intervention [MOMS], comparison group with depressive symptoms [positive], and comparison group without depressive symptoms [negative]) will be calculated for each of the four study time points (baseline [BL], IW6, IW12, postpartum [PP]). A mixed linear model (MLM) will be fit to the data. The model will include one between-subjects effect (Group: MOMS, positive comparison, negative comparison), one within-subject effect (Time: BL, IW6, IW12, PP), and the interaction between group and time. This model will allow estimation of changes from baseline in levels of psychological symptoms within and between groups at each time point. Possible covariates, such as the initiation of UC (medications, psychotherapy), will be fully explored during analysis. Data from participants who drop out of the intervention will be retained in the analytical portion of the study according to intent-to-treat principles. Correlations will be calculated between baby²⁰⁶s birth weight and group (intervention, positive comparison, negative comparison). Figure 2 summarizes data collection timepoints for the study in relation to the archival comparison group database.

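### Attachment is asked about the fetus before birth and about the infant after it, so its within-group change from baseline to postpartum should not be reported as change or used as an effect size

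*Combined protocol and SAP*

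**What the plan says.** Three places in the combined protocol and SAP bear on this.

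- **Research Description, item 4, Maternal Psychological Measures, (f) Maternal-Fetal/Child Attachment.** The MFAS "assesses the extent to which women have an affiliation and interaction with their unborn child (during pregnancy) and their infant (during PP"). One scale is named and its referent changes at delivery.
- **Research Description, item 2, Specific Aim 2.** The outcomes are "maternal psychobehavioral factors (i.e., depressive symptoms, anxiety, ruminations, PA self-efficacy, attachment) at baseline, midpoint and end of the 12-week intervention". Two assessments after delivery follow, one at six weeks and one at 10–20 months. The results are compared with archival data from depressed women in usual care, and the effect sizes are meant to inform later studies.
- **Data Analysis Plan, Aim 2.** The mixed linear model has a group factor, "one within-subject effect (Time: BL, IW6, IW12, PP), and the interaction between group and time". Its stated use is: "This model will allow estimation of changes from baseline in levels of psychological symptoms within and between groups at each time point". The leading outcome is named separately: "with the primary variable of interest, depressive symptoms, measured by the PHQ-9".

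The Comparison Group Data section adds that the archival women were followed into the postpartum period "using psychobehavioral, birth weight, and DNAm measures identical to those proposed in this study".

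The analysis plan says nothing specific about attachment. It gives no separate postpartum model and no equating or invariance check, and it does not say how the scale is worded or scored once the child is born.

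**The concern.** A change from baseline is interpretable when the same quantity is measured twice. For the PHQ-9, the stress scale or the anxiety scale, the woman reports on herself at each visit. For attachment, the baseline answer concerns an unborn child in the second trimester, and the postpartum answer concerns a baby she is caring for. A woman whose disposition has not altered could score differently because the question has a different object.

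The Aim 2 model, applied as written, produces a within-group postpartum-minus-baseline number for attachment. If that number is reported as change, or carried into a later trial as an effect size, it has no single meaning. A larger sample would not help, because the shift is a bias and not noise.

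**Working it through.** **No figure to reproduce.** The documents give no mean, SD, range or expected change for the MFAS. The core of the point is therefore a reading of the text, and the arithmetic only illustrates it.

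**Which contrasts cross the switch.** BL, IW6, IW12 and PP are baseline, intervention weeks 6 and 12, and postpartum.

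| Contrast | Target at start | Target at end | Exposed? |
|---|---|---|---|
| IW6 − BL | fetus | fetus | no |
| IW12 − BL | fetus | fetus | no |
| PP − BL, within group | fetus | infant | yes |
| PP − BL, MOMS minus comparison | fetus | infant | only if the shift differs by group |

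**Formula.** Let δ be the mean shift in score due to the change of target alone.

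- Within a group: observed PP − BL = true change + δ.
- Between groups: observed contrast = true contrast + (δ in MOMS − δ in comparison).

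Take δ as 0.5 SD in both groups and no true change. The within-group figure is then 0.5 SD and the contrast is 0.5 − 0.5 = 0. With 0.5 SD in one group and 0.25 SD in the other, the contrast is biased by 0.5 − 0.25 = 0.25 SD.

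**Illustration of the within-group number.**

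- *Sample size, from the sample size justification:* a target of 40 and past attrition of 20–40%, so 40 × 0.8 = 32 or 40 × 0.6 = 24 women remain.
- *Assumed:* SD 1 at both visits, BL–PP correlation r = 0.5, true change 0, and δ of 0.2, 0.5 or 0.8 SD.
- *SD of change:* √(2 − 2r) = √1 = 1.
- *Noncentrality:* δ√n / √(2 − 2r). For δ = 0.5 and n = 32 this is 0.5 × 5.657 = 2.83.
- *Result:* the chance, from the noncentral t distribution, that the two-sided 95% interval for the change excludes zero.

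| Assumed δ | n = 24 | n = 32 | n = 40 |
|---|---|---|---|
| 0.2 SD | 16% | 20% | 23% |
| 0.5 SD | 65% | 78% | 87% |
| 0.8 SD | 96% | 99% | >99% |

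With no shift the figure is 5%. At n = 32 and δ = 0.5, moving r from 0.3 to 0.7 moves the result from 64% to 94%.

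**A second effect.** If the switch of target also weakens the correlation, say from 0.7 to 0.3, the SD of change rises from √0.6 = 0.77 to √1.4 = 1.18. An effect size standardised on change would then shrink, even where δ cancels between groups.

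**The case against.** The strongest reply is that Aim 2 is a comparison with the archival depressed group. The deliverable is then the group-by-time contrast, and a shift that delivery produces in every woman cancels there. The archival measures are called identical and run into the postpartum period, and nothing in the text suggests unequal shifts. This stands, and it confines the problem mainly to the within-group number. The analysis plan does say that within-group change will be estimated at each time point, so that number will exist unless the plan excludes it.

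A second reply is that no uncontrolled change across birth can be attributed to MOMS for any measure, and the protocol itself acknowledges that it lacks a concurrent randomised control. That is true, but it is a different problem. The other scales at least measure the same thing twice.

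Third, the Aim 2 sentence speaks of psychological symptoms and does not name the MFAS. Table 1 and the instruments are separate uploads that are not in the text reviewed. However, attachment is listed under Maternal Psychological Measures and as an Aim 2 outcome, and no other analysis is given for it. Both the aim and the description of the scale place it before and after birth, so the switch does not depend on Table 1. The postpartum wording does remain unknown.

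Fourth, the percentages follow from shifts that were assumed, and the study is a pilot for estimation and not a test. This is accepted: they show what a given shift would do, not that one of that size exists.

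A reader might go further and infer that the whole attachment analysis is invalid, or that the plan computes a flawed change at 10–20 months. The documents support neither. The prenatal changes share one target and time enters as separate levels, so the postpartum level does not systematically distort them. The model's time factor stops at the postpartum visit, and no change score is specified for the long-term survey.

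**Conclusion.** The point holds in a limited form. As written, the plan yields a within-group postpartum-minus-baseline attachment number that mixes a switch of target with any real change. That number should not be called change or used as an effect size. The prenatal changes are sound in this respect. The between-group contrast at the postpartum visit is sound if the shift is equal in both cohorts and both used the same postpartum wording. The plan asserts identical measures but does not give that wording, and equal shifts are an assumption.

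The size and direction of the shift cannot be obtained from the documents. The 16% to 99% range for 24 to 32 women rests entirely on assumed shifts of 0.2 to 0.8 SD and a correlation of 0.5. The practical weight is modest: feasibility and acceptability are the primary aim, the PHQ-9 leads Aim 2, and attachment is one of five psychobehavioral outcomes. The correction is still worth making, because it is cheap and removes a reported quantity that has no clear meaning.

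**What to change.** In the Data Analysis Plan, Aim 2, add for the MFAS:

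1. Change from baseline is reported only at IW6 and IW12.
2. The 6-week postpartum score is a separate outcome, reported as the MOMS-minus-positive-comparison difference with its 95% confidence interval. Baseline MFAS may enter as a covariate, which does not require the two scores to share a scale. Before this is done, confirm and state that both studies used the same postpartum wording and scoring. Adjustment for baseline does not cure a difference in wording.
3. No within-group change from pregnancy to postpartum is reported.
4. If the 10–20 month score is analysed, it is not expressed as change from the prenatal baseline.

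This uses the same data and the same visits. The cost is a few sentences, one check of the archival instrument, and the loss of a pregnancy-to-postpartum change score for this one secondary measure.
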